1.2 Purpose

The purpose of this study is to demonstrate the impact on progression of structural damage in the spine as measured by the mSASSS in patients with AS. Data from this study will be used to support the submission of an AS label extension to include a claim on radiographic progression.

2 Study objectives and endpoints

2.1 Primary objective

To demonstrate the proportion of subjects on secukinumab (150 mg s.c. or 300 mg s.c.) with no radiographic progression as measured by mSASSS at Week 104 is superior to subjects on GP2017 (adalimumab biosimilar 40 mg s.c.).

2.2 Secondary objectives

1. To demonstrate the change from baseline in mSASSS in subjects on secukinumab (150 mg s.c. or 300 mg s.c.) is superior to GP2017 (adalimumab biosimilar 40 mg s.c.) at Week 104.

[REDACTED]

3 Investigational plan

3.1 Study design

This multicenter study uses a randomized, partially-blinded, active-controlled, parallel-group design in subjects with AS. A screening period (SCR) of up to 10 weeks before randomization will be used to assess eligibility followed by 104 weeks of treatment. Two follow-up visits at Weeks 112 and 120 will occur thereafter.

At baseline (BSL), approximately 837 subjects whose eligibility is confirmed will be randomized to one of three treatment groups (1:1:1).

- Group 1: secukinumab 150 mg [1 x 1.0 mL s.c. plus placebo (1 x 1.0 mL s.c.)] at BSL, Weeks 1, 2 and 3, followed by administration every four weeks starting at Week 4
- Group 2: secukinumab 300 mg (2 x 1.0 mL s.c.) at BSL, Weeks 1, 2 and 3, followed by administration every four weeks starting at Week 4
- Group 3: GP2017 (adalimumab biosimilar) 40 mg (1 x 0.8 mL s.c.) at BSL followed by administration every two weeks

[figure not shown]
Although study treatment (secukinumab vs GP2017) will be provided in an open-label fashion to the subjects, secukinumab study treatment will be blinded to the dose. Subjects in groups 1 and 2 will know that they are on secukinumab, but will be blinded to which treatment arm and will not know whether they are receiving secukinumab 150 mg or 300 mg. Subjects in the GP2017 treatment group will know that they are receiving GP2017 (adalimumab biosimilar) 40 mg. Sponsor blinding is described in [Section 5.4](#).

Although no subject will be restricted from receiving necessary rescue medications for lack of benefit or worsening of disease, if rescue treatment with prohibited medications (as described in [Section 5.5.8](#)) occurs, subjects may remain in the study but must discontinue study treatment. All subjects may remain in the study and should continue study-related assessments up to completion, regardless of whether they continue study treatment or not. Subjects who are deemed not to be benefiting from the study treatment based upon safety and efficacy assessments by the investigator or for any reason on their own accord will be free to discontinue study treatment only or any further participation in the study at any time.

[REDACTED]

Two follow-up visits are to be completed after last administration of study treatment for all subjects, regardless of whether they complete the entire study as planned or discontinue prematurely.

Figure 3-1 Study design

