5.5.6 Rescue medication

Rescue medication is defined as any new therapeutic intervention or a significant change to ongoing therapy made because a subject is experiencing either no benefit from participation in the study or worsening/exacerbation of their disease.

Although no subject will be restricted from receiving necessary rescue medications for lack of benefit or worsening of disease, if treatment with prohibited biologics (as described in [Section 5.5.8](#)) is started, subjects may remain in the study but must discontinue study treatment. Efficacy and safety will be assessed at each on-site study visit, and subjects who are deemed by the investigator not to be benefiting from study treatment, or for any reason on the subject's own accord, will be free to discontinue study participation at any time. Changes in NSAIDs, non-biologic DMARDs and corticosteroid concomitant therapy are permitted as per investigator's and subject's clinical judgment. Please see [Section 5.5.7](#), [Section 5.5.8](#) and [Section 5.6.2](#) for details.

Use of rescue medication must be recorded on the corresponding CRF.

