5.5.7 Concomitant medication

The investigator must instruct the subject to notify the study site about any new medications he/she takes after the subject was enrolled into the study. All medications, procedures and significant non-drug therapies (including physical therapy and blood transfusions) administered after the subject was enrolled into the study must be recorded in the appropriate CRF.

Each concomitant drug must be individually assessed against all exclusion criteria/prohibited medication. If in doubt the investigator should contact the Novartis/CRO medical monitor before randomizing a subject or allowing a new medication to be started.

Guidelines for the use of specific medications are provided below:

Methotrexate

Subjects taking MTX (≤ 25 mg/week) must be on a stable dose for at least 4 weeks before randomization.

Folic acid

Subjects on MTX must be taking folic acid supplementation before randomization and during the study to minimize the likelihood of MTX associated toxicity.

Sulfasalazine

Subjects taking sulfasalazine (≤ 3 g/day) must be on a stable dose for at least 4 weeks before randomization.

Systemic corticosteroids

Treatment with systemic corticosteroids (e.g., oral, intramuscular, i.v., s.c.) is permitted if the dose is stable within the 2 weeks preceding randomization through Week 104, up to a maximum daily dosage of 10 mg prednisone equivalent.

Higher-dose, time-limited corticosteroid courses (bursts) may be permitted for exacerbations of medical conditions unrelated to AS (e.g., asthma, chronic obstructive pulmonary disease (COPD), contact dermatitis) after randomization.

Any change in the dose of systemic corticosteroids during the trial must be recorded on the corresponding CRF.

Intra-articular corticosteroids are not permitted within the 4 weeks preceding randomization. After randomization, no more than 1 joint per 24-week period may be injected. No single injection should exceed 40 mg of triamcinolone (or equivalent) and the total dose of intra-articular corticosteroid may not exceed 80 mg of triamcinolone (or equivalent) during any 52-week period. Injection of intra-articular steroids is not permitted within 8 weeks prior to Weeks 16, 52 and 104.

Non-steroidal anti-inflammatory drugs (NSAIDs) (including COX-1 or COX-2 inhibitors) and acetaminophen/paracetamol

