5.5.8 Prohibited medication

Use of the treatments displayed in [Table 5-1](#) is NOT allowed after the start of the washout period through Week 104, unless otherwise specified below.

Live vaccines should not be given until 12 weeks after last study treatment administration of secukinumab. The elimination of adalimumab may take up to four months ([Humira® SmPC](#)); live vaccines should not be given until 16 weeks after last study treatment administration of GP2017.

Table 5-1 Prohibited medication

Medication	Washout period (before randomization)	Action (after randomization, through Week 104)
Any immunomodulating biologic drugs, including but not limited to TNF α inhibitors, denosumab, secukinumab, or other biologic drug directly targeting IL-17 or IL-17 receptor	No prior exposure	Discontinue study treatment
Any cell-depleting therapies including but not limited to anti-CD20 or investigational agents	No prior exposure	Discontinue study treatment
Any investigational treatment or participation in any interventional study	4 weeks or 5 half-lives (whichever is longer)	Discontinue study treatment
Live vaccinations	6 weeks	Through Week 120, interrupt study treatment 12 weeks for secukinumab and 16 weeks for GP2017
Stable use of systemic corticosteroids > 10 mg prednisone equivalent	2 weeks	Protocol deviation
Intra-articular corticosteroids	4 weeks	Dose adjustments permitted after randomization
Unstable dose of conventional synthetic DMARDs (e.g. MTX, sulfasalazine)	4 weeks	Dose adjustments permitted after randomization; no more than 1 DMARD concomitantly
Non-biologic targeted synthetic DMARDs (e.g. JAK inhibitors) (van der Heijde 2016)	4 weeks	Protocol deviation

Medication	Washout period (before randomization)	Action (after randomization, through Week 104)
Unstable dose of NSAIDs (COX1 or COX2 inhibitors), paracetamol/acetaminophen or low strength opioids	2 weeks	Dose adjustments permitted after randomization
Analgesics (other than NSAIDs, paracetamol/acetaminophen or low strength opioids)	4 weeks	Protocol deviation

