5.6.2 Discontinuation of study treatment

Discontinuation of study treatment for a subject occurs when study drug is stopped earlier than the protocol planned duration, and can be initiated by either the subject or the investigator.

Subjects may voluntarily discontinue study treatment (refuse study treatment but continue with study participation) or completely discontinue from the study (no further study participation) for any reason, at any time.

The investigator must discontinue study treatment for a given subject if, on balance, he/she believes that continuation would negatively impact the risk/benefit of study participation.

Study treatment must be discontinued under the following circumstances:

- Subject wish
- Withdrawal of consent
- Pregnancy (see [Section 6.5.9](#) and [Section 7.6](#))
- Any situation in which study participation might result in a safety risk to the subject
- Emergence of the following adverse events:
 - Any severe or serious adverse event that in the judgement of the investigator, taking into account the subject's overall status prevent the subject from continuing study treatment
 - Life-threatening infection
 - Any laboratory abnormalities that in the judgment of the investigator, taking into consideration the subject's overall status, prevent the subject from continuing study treatment (A general guidance on clinically notable laboratory values is provided in [Appendix 1](#).)
- Use of any prohibited treatment as per recommendations in [Table 5-1](#)

The investigator must determine the primary reason for the subject's premature discontinuation of study treatment and record this information on the appropriate CRF.

The investigator must also contact the IRT to register the subject's discontinuation from study treatment.

Discontinuation of study treatment does not require the subject to be discontinued from the study and all ongoing visit assessments. Refer to [Section 6](#) for the visit schedule and assessments.

If study drug discontinuation occurs because of treatment unblinding, please refer to [Section 5.5.9](#).

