### 2.5.3 Handling of missing values/censoring/discontinuations

Missing Week 104 data for a given subject who discontinued in the study will be imputed using an imputation model based on the observed data of subjects in the same randomized arm who also discontinued study treatment but for whom Week 104 X-ray data are available ('retrieved dropout approach', [EMA 2010](#)) and based on the observed data of the given subject.

A logistic regression model will be fitted to the Week 104 X-ray data for the retrieved dropout patients, while adjusting for treatment, baseline mSASSS and post-baseline slope in mSASSS.

The post-baseline slope is defined as the last available post-baseline change in mSASSS score divided by study day on which the X-ray was taken. Recent literature suggests that in AS patients treated with TNF inhibitors the spinal radiographic progression followed a linear course during the first 4 years of follow-up (Maas, et. al. 2017). Thus, the linearity assumption is expected to be reasonable. The covariates of baseline mSASSS and slope will be standardized to have a mean of 0 and standard deviation of 1 before model fitting.

PROC MCMC will be used for fitting the logistic regression model and multiple imputation of the Week 104 value, with weakly informative priors and model code as shown below,

```
prior beta1 ~ normal(0,sd=2);
```

```
prior beta2 ~ normal(0,sd=2);
```

```
prior beta3 ~ normal(0,sd=2);
```

```
prior beta4 ~ normal(0,sd=3);
```

```
prior beta5 ~ normal(0,sd=3);
```

```
pi = logistic(beta1*trt_GP2017 + beta2*trt_SEC150 + beta3*trt_SEC300 +  
beta4*sqrt(base_stand) + beta5*slope_stand);
```

```
model noprog ~ binary(p = pi);
```

where trt\_GP2017 – binary indicator for GP2017 40 mg

trt\_SEC150 – secukinumab 150 mg

trt\_SEC300 – secukinumab 300 mg

sqrt(base\_stand) – square root of the baseline mSASSS (standardized)

slope\_stand – the last available post-baseline change in mSASSS score divided by study day on which the X-ray was taken (standardized)

noprog – no radiographic progression at Week 104

If all post-baseline values are missing for a subject, the subject will be imputed based on a similar model as above but just based on treatment and baseline value as covariates (without the post-baseline slope variable). Subjects with a missing baseline will be excluded from the analysis.

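### The protocol gives conflicting instructions on which rescue treatments require study drug to stop, and on whether systemic steroids may change

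*Protocol*

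**What the plan says.** **When study drug must stop**

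- Protocol 3.1: the trigger is "if rescue treatment with prohibited medications" as described in Section 5.5.8, and the consequence is that "subjects may remain in the study but must discontinue study treatment". No class of prohibited medication is exempted.
- Protocol 5.5.6 has a nearly parallel sentence citing the same Section 5.5.8, but the trigger is "if treatment with prohibited biologics".
- Protocol 5.5.8, Table 5-1, assigns an action to each class. Three rows require discontinuation: immunomodulating biologics, cell-depleting therapies, and investigational treatments. Live vaccination leads to interruption. Three rows are labelled a protocol deviation and mention no stop: the row beginning "Non-biologic targeted synthetic DMARDs (e.g. JAK inhibitors", stable systemic corticosteroids above 10 mg prednisone equivalent, and analgesics other than the listed types. The remaining rows permit dose adjustment.
- Protocol 5.6.2 includes among the mandatory stops "Use of any prohibited treatment as per recommendations in" Table 5-1.

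**Whether steroids may change**

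- Protocol 5.5.6, on lack of benefit or worsening: "Changes in NSAIDs, non-biologic DMARDs and corticosteroid concomitant therapy are permitted" according to clinical judgment. The paragraph ends by referring to 5.5.7, 5.5.8 and 5.6.2 for details.
- Protocol 5.5.7: systemic corticosteroid treatment "is permitted if the dose is stable within the 2 weeks preceding randomization through Week 104", up to 10 mg prednisone equivalent daily. Higher, time-limited bursts are allowed only for conditions other than AS. Dose changes must be recorded.

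**Where stopping enters the analysis**

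- SAP 2.5.3 draws imputation donors from subjects in the same arm "who also discontinued study treatment but for whom Week 104 X-ray data are available".
- SAP 2.4.1, 2.8.1, 2.8.2 and 2.8.3.1 end exposure, treatment-emergent events, laboratory data and vital signs at or by reference to last dose plus 84 days.
- SAP 2.5.4 and 2.6.4 offer a supplementary hypothetical estimand that names biologic rescue only.

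**The concern.** An investigator with a worsening patient needs one answer to two questions: does study drug stop if this medicine is added, and may the steroid dose change? The protocol gives more than one answer to each. Roughly 200 centers are planned (Protocol Section 4), so different sites can in good faith follow different sections.

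Three things are at stake. The first is patient safety: whether study drug continues alongside another immunomodulator can depend on which section was read. The second is comparability: investigators know whether a patient is on secukinumab or GP2017 (Protocol 5.4), so discretion created by unclear rules could be used differently between arms. The third is analysis: who actually stops determines the end of exposure, the safety windows and the pool of subjects who can serve as retrieved-dropout donors. Deviation tables under SAP 2.3.1 also depend on which section is taken to define a deviation.

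**Working it through.** This is mainly a comparison of texts. Section 5.5.6 defines rescue as a new intervention, or a significant change to ongoing therapy, because of no benefit or worsening. A medicine started for an AS flare is therefore rescue under the protocol's own definition.

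| Event after randomization | Section 3.1 | Section 5.5.6 | Table 5-1 |
|---|---|---|---|
| Another biologic as rescue | Stop | Stop | Stop |
| Non-biologic investigational agent as rescue | Stop | No stop stated | Stop |
| JAK inhibitor as rescue | Stop | No stop stated; can be read as a permitted non-biologic DMARD change | Deviation, no stop |
| Stable systemic steroid above 10 mg for AS | Stop | Steroid change permitted by judgment | Deviation, no stop |
| Prohibited analgesic as rescue | Stop | No stop stated | Deviation, no stop |

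The deviation rows are squarely caught by 3.1. Section 5.5.8 prohibits everything in the table unless the table says otherwise. Permitting dose adjustment says otherwise; calling use a deviation does not. Those rows are prohibited medications, and 3.1 attaches a mandatory stop to them.

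For systemic steroids, take a rise for an AS flare that stays within 10 mg. Section 5.5.6 permits it. Section 5.5.7 does not, because the dose is no longer stable and the burst exception excludes AS. Table 5-1 has no row for it.

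**Planning figures that depend on discontinuation** (Protocol 9.7, SAP Section 3)

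- Blended secukinumab rate: 0.80 × 66% + 0.20 × 51% = 52.8% + 10.2% = 63.0%, as stated.
- Power per dose = Φ{[d − z·√(2p̄(1−p̄)/n)] / √[(p₁(1−p₁) + p₀(1−p₀))/n]}, with n = 279, p₁ = 0.63, p₀ = 0.51, p̄ = 0.57, d = 0.12 and z = 2.241 (two-sided 0.025). This is Φ{(0.1200 − 0.0940)/0.0416} = 73.4% (stated 73%).
- Power for at least one dose under Hochberg, by simulation with 400,000 runs: 87.9% (stated 88%).

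These reproduce, so no stated figure is in dispute.

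**What can be said about size**

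- Each extra percentage point of discontinuation is 0.01 × 279 ≈ 2.8 subjects per arm, and lowers the blended rate by 0.01 × (66 − 51) = 0.15 points. With assumed discontinuation of 10%, 20% and 30%, the rate is 64.5%, 63.0% and 61.5%, and per-dose power is 84%, 73% and 60%. The rates other than 20% are assumptions. Nothing says how far conflicting stop rules would move the rate.
- SAP 2.5.3 drops treatment from the imputation model if any arm has fewer than 8 donors. The planning assumption leaves 0.20 × 279 ≈ 56 per arm who do not both complete treatment and provide evaluable films. If all 56 were treatment discontinuers (an assumption), the fallback would need at most 7/56 = 12.5% to be retrieved. The documents give no retrieval rate.

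**The case against.** The strongest reply is that Section 3.1 is a summary, that it refers to 5.5.8, and that Table 5-1 is the operative text. On that view one loose sentence is out of line, and for added biologics all the sections agree. The agreement on biologics stands. The rest does not cure the conflict: 3.1 states a mandatory stop without qualification, and nothing says that the table prevails.

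Several stronger readings are tempting, and the documents do not support them.

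- *The same patient's record could be classed as on or off treatment.* No. The protocol glossary defines treatment discontinuation as permanently stopping before the planned end. Section 5.6.2 requires the reason on the CRF and registration in the IRT, and SAP 2.5.3 uses subjects who did stop. A patient starting a JAK inhibitor is a potential donor only after actually stopping and only with a Week 104 X-ray. Conflicting rules can change what happens to the patient, not how a given record is read.
- *Section 5.6.2 is a further contradictory stop rule.* Its wording most naturally defers to the table's action column. It could be clearer, but it need not conflict.
- *The intra-articular steroid rules conflict.* Permission to adjust in Table 5-1 is compatible with adjusting within the 5.5.7 limits.
- *Any steroid change is a deviation under one section.* Table 5-1 labels only stable use above 10 mg that way, and 5.5.7 anticipates changes by asking for them to be recorded. The cross-reference at the end of 5.5.6 also softens its general permission. What survives is the requirement in 5.5.7 for stability through Week 104, with no exception for AS.
- *Reclassifying a few subjects would switch the imputation model.* No donor counts are given, and nothing shows that they would lie near 8.

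**Conclusion.** The protocol is wrong as written on two points. Sections 3.1, 5.5.6 and Table 5-1 do not agree on which rescue medications require study drug to stop; the JAK inhibitor case is the clearest. Sections 5.5.6 and 5.5.7 do not agree on whether systemic steroids may change for worsening AS. Both conflicts are in current text.

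The consequence runs through site behavior: who actually stops, hence the exposure and safety windows and, indirectly, who is available as a donor. Its size cannot be estimated, because the documents do not say how many subjects receive these medicines or how sites resolved the conflict. The effect on the primary result is limited by design. The estimand is regardless of adherence (SAP 2.5.1), so an observed Week 104 X-ray counts whatever the treatment status, and only imputed values could be touched. The point should be fixed because it is specific, cheap and bears on patient management, not because a bias has been shown.

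**What to change.** **Protocol.** Reconcile 3.1, 5.5.6, 5.5.7 and Table 5-1 into one action per medication class, state it in one place, and have the other sections refer to it. Section 5.6.2 should say explicitly that it follows the reconciled action column. Which action applies to each class, and what steroid rule applies, is for the sponsor's clinical team to decide.

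**SAP.** Keep the donor set based on the recorded actual stop of study treatment. It should not be redefined by what a medication rule would have required, since that would label subjects by what should have happened. In the supplementary hypothetical-estimand analyses (2.5.4 and 2.6.4), flag targeted synthetic DMARD rescue alongside biologic rescue.

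**Cost.** A protocol clarification or letter to sites, and a short SAP addition before database lock. No new data are needed: rescue use, steroid dose changes, concomitant medication and dosing dates already go on the CRF (Protocol 5.5.6, 5.5.7, 6.3). All subjects had completed Week 52 by Amendment 2, so a site clarification after that reaches only the remaining treatment period. The SAP change keeps its full value.

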3.2 Rationale for study design

The subject population will be described in more detail in the [Section 4](#) below.

The randomized, partially-blinded, active-controlled, parallel-group design used in this study is based on the primary focus of this study, which is to demonstrate the ability of secukinumab to slow structural spinal progression over time relative to current standard of care for AS. The primary objective is based on mSASSS scoring of spinal X-rays obtained at baseline and Week 104, which will be conducted in a fully blinded fashion in this study with a partially-blinded design. Spinal structural progression in AS is known to be a slow process. Thus, the length of the study is required to be 2 years in order to detect radiographic changes and fully demonstrate the potential impact of therapy.

Evaluations of mSASSS scoring for the primary objective will be conducted by three independent readers who will be blinded to the subject name, subject initials, exam date, order of image acquisition, investigator site identifiers, study treatment group, and all other efficacy and safety assessments. As previously noted, a partially-blinded design will not bias the analysis of the primary or secondary radiographic endpoints, which are not subject or physician reported outcomes.

Adalimumab is a commonly used anti-TNF agent in AS and confers similar efficacy to secukinumab in terms of signs and symptoms ([van der Heijde 2006](#)). Radiographic progression data for AS subjects on adalimumab for up to 2 years are published and provide statistical

assumptions for the powering of the primary endpoint ([van der Heijde 2009](#)). Thus, adalimumab is well suited as the active comparator in this study.

While the GP2017 (adalimumab biosimilar) treatment group will be supplied with unblinded study medication, the secukinumab treatment groups will be blinded to the dose of secukinumab through the use of a blinded placebo injection in the 150 mg s.c. group. The blinding of the secukinumab treatments (150 mg or 300 mg) will allow for an evaluation of a potential dose-response of the 150 mg and 300 mg secukinumab doses on both efficacy and safety outcomes.

